### **Time-to-Deterioration (TTD)**

The Kaplan-Meier method will be used to estimate the TTD curve for each treatment group. The estimate of median TTD and its 95% confidence interval will be obtained from the Kaplan-Meier estimates. The treatment difference in TTD will be assessed by the stratified log-rank test. A stratified Cox proportional hazard model with Efron's method of tie handling and with a single treatment covariate will be used to assess the magnitude of the treatment difference (ie, HR). The HR and its 95% CI will be reported. The same stratification factors used for randomization (see Section 6.3.2) will be used as the stratification factors in both the stratified log-rank test and the stratified Cox model.

### **9.6.4 Demographic and Baseline Characteristics**

The comparability of the treatment groups for each relevant demographic and baseline characteristic will be assessed by the use of tables and/or graphs. No statistical hypothesis tests will be performed on these characteristics. The number and percentage of participants screened and randomized and the primary reasons for screening failure and discontinuation will be displayed. Demographic variables, baseline characteristics, primary and secondary diagnoses, and prior and concomitant therapies will be summarized by treatment either by descriptive statistics or categorical tables.

### **9.7 Interim Analyses**

The eDMC will serve as the primary reviewer of the results of the interim analyses and will make recommendations for discontinuation of the study or modification to the EOC of the Sponsor. If the eDMC recommends modifications to the design of the protocol or discontinuation of the study, this EOC and potentially other limited Sponsor personnel may be unblinded to the treatment-level results in order to act on these recommendations. The extent to which individuals are unblinded with respect to results of interim analyses will be documented by the unblinded team. Additional logistic details will be provided in the eDMC Charter.

Treatment-level results of the interim analyses will be provided by the unblinded statistician to the eDMC. Prior to final study unblinding, the unblinded statistician will not be involved in any discussions regarding modifications to the protocol or statistical methods, identification of protocol deviations, or data validation efforts after the interim analyses.

#### **9.7.1 Efficacy Interim Analyses**

CCI

CCI

### **9.7.2 Safety Interim Analyses**

The eDMC will conduct regular safety monitoring. The timing of the safety monitoring will be specified in the eDMC charter. eDMC monitoring for safety will be conducted at a minimum every 6 months until such time that the eDMC determines that monitoring at a different frequency is appropriate.

## 9.8 Multiplicity

CCI

### 9.8.1 Overall Survival

CCI

CCI

CCI

CCI

CCI

[figure not shown]

### 9.8.2 Progression-free Survival

CCI

[figure not shown]

CCI

[figure not shown]

### 9.8.3 Objective Response Rate

No initial alpha is allocated to test ORR. If superiority for all PFS and OS hypotheses (H1, H2, H3, H4 and H5) are declared, CCI

[figure not shown]

CCI

[figure not shown]
### 9.8.4 Safety Analyses

The eDMC has responsibility for assessment of overall risk/benefit. When prompted by safety concerns, the eDMC can request corresponding efficacy data. CCI

### 9.9 Sample Size and Power Calculations

CCI

CCI

CCI

## 9.10 Subgroup Analyses

CCI

### **9.11 Compliance (Medication Adherence)**

Drug accountability data for study treatment will be collected during the study. Any deviation from protocol-directed administration will be reported.

### **9.12 Extent of Exposure**

Extent of exposure for a participant is defined as the number of cycles in which the participant receives the study intervention. Summary statistics will be provided on the extent of exposure for the APaT population.

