#### **Initial Treatment Phase**

Overall, approximately 1246 participants will be randomized 1:1 to:

- MK-7684A (Arm 1)
- Pembrolizumab (Arm 2)

No treatment crossover is planned for the study. The study design is shown in [Figure 1](#) (Initial Treatment) and [Figure 2](#) (Second Course).

Participants will be evaluated with radiographic imaging to assess response to study intervention every 9 weeks from randomization through 54 weeks, then every 12 weeks until confirmed PD or initiation of a new anticancer regimen. All imaging obtained during the initial treatment phase of the study will be submitted to the iCRO for BICR, which will assess the images using RECIST 1.1 for determination of PFS, OR, and DOR. Tumor imaging showing site-assessed PD should be submitted immediately for verification by BICR

before study intervention discontinuation. Once disease progression is verified centrally, subsequent imaging (if acquired) should not be submitted to the iCRO.

Participants receiving MK-7684A or pembrolizumab may be permitted to continue study intervention beyond PD verified by BICR per RECIST 1.1 if the treating investigator considers that the participant may experience clinical benefit with continued treatment and the participant is clinically stable and tolerating study intervention; however, this decision must be approved by the Sponsor. If the investigator recommends continuation of study intervention beyond disease progression, the participant or legally acceptable representative will be asked to provide a new documented informed consent.

Survival follow-up will continue after PD, discontinuation of study intervention, and the start of new anticancer treatment. In addition, upon Sponsor request, participants may be contacted for survival status at any time during the study.

AE monitoring will be ongoing throughout the study. AEs will be graded in severity according to the guidelines outlined in the NCI CTCAE, version 5.0.

Treatment with MK-7684A or pembrolizumab will continue for up to 35 treatment cycles, or until a discontinuation criterion is met (see Section 7.1). Treatment may be discontinued for participants with a confirmed CR (see Section 6.6.2).

**CCI** for this study. Details regarding interim analyses are provided in Section 9.7.

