- Those participants remaining on study at the time of Amendment 06 should continue to be monitored in the study through the AE reporting period (Section 8.4).

- Participants may enroll in an extension study, if available.
  - Participation in this study is ended when the participant is consented for an extension study.
  - The overall study ends when the last participant completes the last study-related contact, withdraws consent, or is lost to follow-up (Section 7.3), or the last participant on active treatment is consented in an extension study.
  - For participants who enter an extension study, all AEs, SAEs, and other reportable safety events must be reported by the investigator in this protocol (parent study) from the time of intervention randomization up to the time of providing documented informed consent for an extension study. Note: Once consented to an extension study, safety events, including those considered related to study intervention, will be collected as instructed in the extension study.

Existing protocol content is retained for historical reference.

Study intervention is defined as any investigational intervention(s), marketed product(s), placebo, or medical device(s) intended to be administered to a study participant according to the study protocol.

Clinical supplies (MK-7684A and pembrolizumab) will be packaged to support enrollment. Clinical supplies will be affixed with a clinical label in accordance with regulatory requirements.

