## **6.1 Study Intervention(s) Administered**

The study intervention(s) are in [Table 4](#).

Country-specific requirements are noted in [Appendix 7](#).

Table 4 Study Interventions

Arm Name	Arm Type	Intervention Name	Intervention Type	Dose Formulation	Unit Dose Strength(s)	Dosage Level(s)	Route of Administration	Regimen/ Treatment Period/ Vaccination Regimen	Use	IMP or NIMP / AxMP	Sourcing
Arm 1	Experimental	MK-7684A	Biological/Vaccine	Solution	MK-7684 200mg + pembrolizumab 200mg/ 20 mL vial	200 mg/ 200 mg	IV Infusion	q3w up to 35 cycles	Test Product	IMP	Central
Arm 2	Active comparator	Pembrolizumab	Biological/vaccine	Solution	25 mg/ml	200 mg	IV infusion	q3w up to 35 cycles	Comparator	IMP	Central
All participants	Experimental	Pembrolizumab	Biological/vaccine	Solution	25 mg/ml	200 mg	IV infusion	q3w	Test Product	IMP	Central

IMP = investigational medicinal product; MK-7684A = Coformulated as 200 mg MK-7684 and 200 mg pembrolizumab; NIMP/AxMP = noninvestigational/auxiliary medicinal product.

The classification of IMP and NIMP/AxMP in this table is based on guidance issued by the European Commission and applies to countries in the European Economic Area (EEA). Country differences with respect to the definition/classification of IMP and NIMP/AxMP may exist. In these circumstances, local legislation is followed.

All study interventions will be administered on an outpatient basis.

All products indicated in [Table 4](#) will be provided centrally by the Sponsor or locally by the study site, subsidiary, or designee, depending on local country operational or regulatory requirements.

For any commercially available product that is provided by the study site, subsidiary, or designee, every attempt will be made to source these supplies from a single lot/batch number. The study site is responsible for recording the lot number, manufacturer, and expiry date for any locally purchased product as per local guidelines unless otherwise instructed by the Sponsor.

Refer to Section 8.1.8 for details regarding administration of the study intervention.

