## 9 KEY STATISTICAL CONSIDERATIONS

Upon receipt of investigator letter detailing discontinuation of the MK-7684A clinical program, the following changes apply. The changes listed below supersede any protocol content/instructions from previous amendments.

- This study is closed to enrollment. This study has enrolled 1264 participants.
- This study will be unblinded.
- The estimated duration of study was updated from 6 years to 5 years.
- Participants receiving MK-7684A will be transitioned to pembrolizumab.
- Pembrolizumab can be sourced locally or centrally.
- Participants with access to approved SOC (eg, immunotherapy, chemotherapy, targeted therapy, as monotherapy or in combination) should be considered for discontinuation from the study. Those benefiting from pembrolizumab with, but unable to access it as SOC outside the study, may continue on study and receive treatment with pembrolizumab until discontinuation criteria are met. The final required study visit will be the Safety Follow-up Visit.
- Imaging scans should no longer be submitted to iCRO nor read by BICR. However, for participants who are still on study treatment and deriving clinical benefit and will continue study treatment until criteria for discontinuation are met, local tumor imaging should continue per local SOC schedule and local SOC method of assessment of imaging. All imaging as well as relevant objectives and endpoints will be assessed locally.
- PK/ADA samples will no longer be collected.
- Biomarker FBR samples will no longer be collected.
- ePROs will no longer be collected.
- Treatment beyond progression will no longer be offered. Any participant already receiving treatment beyond progression will be able to complete treatment as planned.
- Participants who complete study treatment or otherwise meet EOT criteria will be discontinued from the study after the EOT visit and any required safety follow-up visit.
- The futility interim analysis (IA1) was conducted. The pre-specified efficacy interim analysis (IA2) and final analysis outlined in the SAP will not be conducted.
- Selected analyses of safety and endpoints will be performed at the end of the study.
- There will be no follow-up for survival status. Participants currently in imaging follow up should obtain imaging and further oncological care as per local standard of care. However, standard safety reporting should continue, as applicable.

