- Those participants remaining on study at the time of Amendment 06 should continue to be monitored in the study through the AE reporting period (Section 8.4).

- Participants may enroll in an extension study, if available.
  - Participation in this study is ended when the participant is consented for an extension study.
  - The overall study ends when the last participant completes the last study-related contact, withdraws consent, or is lost to follow-up (Section 7.3), or the last participant on active treatment is consented in an extension study
  - For participants who enter an extension study, all AEs, SAEs, and other reportable safety events must be reported by the investigator in this protocol (parent study) from the time of intervention randomization up to the time of providing documented informed consent for an extension study. Note: Once consented to an extension study, safety events, including those considered related to study intervention, will be collected as instructed in the extension study.

Existing protocol content is retained for historical reference.

This section outlines the statistical analysis strategy and procedures for the study. If, after the study has begun, but prior to any unblinding/final database lock, changes are made to primary and/or key secondary hypotheses, or the statistical methods related to those hypotheses, then the protocol will be amended (consistent with ICH Guideline E-9). Changes to exploratory or other nonconfirmatory analyses made after the protocol has been finalized, but prior to unblinding/final database lock, will be documented in a supplemental SAP (sSAP) and referenced in the Clinical Study Report (CSR) for the study. Post hoc exploratory analyses will be clearly identified in the CSR. Separate analysis plans (ie, separate documents from the sSAP) will be developed to detail PK and biomarker analyses. The ePRO analysis plan will be included in the sSAP.

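### Does Section 9.12 misstate MK-7684A exposure once Amendment 06 moves Arm 1 to pembrolizumab?

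*Combined protocol and SAP*

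**What the plan says.** Section 9.12 defines exposure in one sentence: "Extent of exposure for a participant is defined as the number of cycles in which the participant receives the study intervention". It then asks for summary statistics in the APaT population. It names no arm, does not separate products and sets no cut-off date.

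Two other places fix what counts as study intervention. Section 6 states: "Study intervention is defined as any investigational intervention(s), marketed product(s), placebo, or medical device(s) intended to be administered to a study participant". Section 6.1 says "The study intervention(s) are in" Table 4, and that table now has a pembrolizumab row for all participants as well as the rows for Arm 1 and Arm 2.

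The Amendment 06 list at the head of Section 9 says "Participants receiving MK-7684A will be transitioned to pembrolizumab". It cancels IA2 and the final analysis and keeps a smaller commitment: "Selected analyses of safety and endpoints will be performed at the end of the study". Participants who can obtain approved standard of care "should be considered for discontinuation from the study", and "Participation in this study is ended when the participant is consented for an extension study". The list overrides earlier instructions, and the text that follows it is kept as a historical record.

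On grouping, Section 9.5.2 analyses participants by treatment actually received. The only regrouping it describes is for someone on the wrong treatment for the whole treatment period. In the visible part of Section 9.6.2, the only cut-off for the primary safety analyses is the start of Second Course.

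**The concern.** The exposure and safety rules come from a design in which, according to Section 4.1, "No treatment crossover is planned for the study". Amendment 06 then introduced a one-way switch: Arm 1 changes product and Arm 2 does not. Read literally, 9.12 adds a switcher's pembrolizumab cycles to the MK-7684A cycles. Section 9.5.2 does not move that participant out of the MK-7684A group, because a switch directed by the protocol is not incorrect treatment. An exposure table by arm could therefore show cycles without MK-7684 under an MK-7684A heading, and the error would run in one direction only.

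Adverse events raise a similar question. They are collected until 30 days after study intervention ends (Section 8.4.1), so events after the switch reach the database, and no visible rule says how to label them. The sponsor stopped MK-7684A because it judged the benefit-risk balance unfavourable, so a clear exposure and safety record for that product matters.

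**Working it through.** **Step 1: what the text implies for one participant.** The plan states no figure for this, so there is none to reproduce. Let k be MK-7684A cycles and m be pembrolizumab cycles after the switch. Exposure under 9.12 is k + m, MK-7684A exposure is k, and the difference is m. A participant with k = 22 who completes the 35 treatments of Section 6.6.2 has m = 35 − 22 = 13, which is 13/22 = 59% more than k. That example is chosen, not typical.

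**Step 2: how many could have switched in the first course.**
- From the documents: 1264 enrolled 1:1, so about 632 in Arm 1. There are 35 doses at 21-day intervals, so the last falls on day 34 × 21 = 714, or 714/30.44 = 23.5 months. The original protocol (19-OCT-2020) and Amendment 06 (29-JAN-2025) are 51.4 months apart.
- Assumed: letter at L = 45 to 51 months after first randomization, uniform accrual over A = 24 to 34 months, exponential time on treatment with median t = 4 to 8 months, and nobody leaving at the letter.

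Time since randomization at the letter is uniform between L − A and L. A participant can switch only if that time is under 23.5 months and treatment is still running:

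N ≈ (632/A) × (t/ln 2) × [2^(−(L−A)/t) − 2^(−23.46/t)]

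| L / A / t (months) | Formula | Simulation with whole doses | Share of Arm 1 cycles |
|---|---|---|---|
| 45 / 30 / 6 (middle) | 21.07 × 8.656 × (0.1768 − 0.0665) = 20.1 | 19 | 1.4% |
| 45 / 34 / 8 (largest) | 18.59 × 11.54 × (0.3856 − 0.1310) = 54.6 | 53 | 4.4% |
| 48 / 24 / 6 | L − A = 24, above 23.5, so 0 | 0 | 0% |

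The formula runs slightly high because it counts people who have no further dose due. In the middle case switchers average 27.4 MK-7684A doses before and 5.7 pembrolizumab doses after, so their 9.12 total exceeds k by 5.7/27.4 = 21%. If half of those eligible leave for standard of care or an extension study, the largest case falls to 27 switchers and 2.3% of cycles. If 80% leave, it falls to 11 and 0.9%.

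**Step 3: effect on the percentage with at least one event.** Only a first event after the switch changes that percentage. For a constant hazard h, the rise is roughly

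(N/632) × exp(−h × time before) × [1 − exp(−h × time after)]

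Middle case, 50% incidence at 12 months: h = ln 2/12 = 0.058 per month. Time before is 27.4 × 0.69 = 18.9 months. Time after, to 30 days past the last dose, is 4.7 × 0.69 + 0.99 = 4.2 months. The result is 0.031 × 0.336 × 0.216 = 0.0022, or 0.22 percentage points. Participant-level summation over 12-month incidences from 2% to 90% gives a maximum of 0.22 points in the middle case and 0.94 points in the largest.

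**Step 4: does 9.12 govern a remaining analysis?** It governs only if the sponsor includes an exposure summary by arm among the selected analyses. The visible text neither includes nor excludes one.

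**The case for a change.** The strongest argument for a change is that Amendment 06 overrides older content but supplies no exposure or grouping rule of its own. If any safety analysis is run, Sections 9.5.2, 9.6.2 and 9.12 are then the only visible rules for it. Section 9.12 is not redacted, the literal reading does give k + m, and one sentence would settle the matter. Section 9.11 would not reveal the switch, since it reports departures from protocol-directed administration and the switch is not one.

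The reading of the text stands, and so does the advice to show the two products separately. The case for amending the plan does not stand, for three reasons.

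- Total cycles of study intervention is a legitimate description of treatment given. A split by product adds to it and corrects nothing. Section 6.4 has each dose date and time recorded in the CRF, and drug accountability data (Section 9.11) identify the product, so the split needs no new data.
- No wrong rule is shown for events. Parts of 9.6.2 and the content of Table 11 are not visible, and the sSAP is not among the documents. Late immune-related events may arise months after the last dose (Section 6.6.1), so events after the switch should stay in the Arm 1 summary in any case. The most that could be asked for is one extra table.
- Editing Section 9 would mean a protocol amendment, with regulatory and ethics review, for a terminated study that is already due to be unblinded.

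The size estimate also has a gap. It stops at dose 35, so anyone receiving Second Course MK-7684A at the switch, with up to 17 further cycles allowed, is left out. The 4.4% is therefore a first-course figure under stated assumptions and not a ceiling.

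**Conclusion.** No change to the plan is needed. Section 9.12 is silent on a switch that did not exist when the rule was designed, and analysts can handle that when they report. If exposure is summarized by arm, the study report should list MK-7684A cycles and post-switch pembrolizumab cycles separately for Arm 1. This can be recorded in the sSAP if unblinding and lock have not occurred, and otherwise labelled post hoc in the CSR, as the opening of Section 9 already provides.

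The number of switchers is not given and may be zero. With L of 45 to 51 months, accrual over 24 to 34 months, median treatment of 4 to 8 months and no exits, the first-course effect is 0 to 53 participants and 0 to 4.4% of Arm 1 cycles. Any at-least-one-event percentage would rise by less than one point. A letter at month 42, outside that range, would give at most 7.5% of cycles. The safety confidence intervals are descriptive, none of H1 to H6 is touched, and effects of this size would not be expected to alter a safety conclusion. The point about how post-switch events are displayed is not established on the visible text.

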## 10 SUPPORTING DOCUMENTATION AND OPERATIONAL CONSIDERATIONS

### 10.1 Appendix 1: Regulatory, Ethical, and Study Oversight Considerations

#### 10.1.1 Code of Conduct for Interventional Clinical Trials

##### Merck Sharp & Dohme LLC, Rahway, NJ, USA (MSD)

#### I. Introduction

##### A. Purpose

Merck Sharp & Dohme LLC, Rahway, NJ, USA (MSD), through its subsidiaries, conducts clinical trials worldwide to evaluate the safety and effectiveness of our products. As such, we are committed to designing, planning, conducting, analyzing, and reporting these trials in compliance with the highest ethical and scientific standards. Protection of participants in clinical trials is the overriding concern in the design and conduct of clinical trials. In all cases, MSD clinical trials will be conducted in compliance with MSD's global standards, local and/or national regulations (including all applicable data protection laws and regulations), Regulation (EU) 536/2014, the International Council for Harmonisation Good Clinical Practice (ICH GCP) E6 and ICH General Considerations for Clinical Studies E8, and in accordance with the ethical principles that have their origin in the Declaration of Helsinki.

